## INVESTIGATOR STUDY PLAN - REQUIRED

$Y = b0 + b1*int\_pr + b2*fu\_pr + b3*e + b4*int\_pr*e + b5*fu\_pr*e + \text{other predictors (p\_chars, c\_chars, clinician, study site, etc.)} + \text{random effects}$

Where:  $Y$  = alcohol use dependent variable;  $int\_pr$  = 1 for intervention period, = 0 otherwise;  $fu\_pr$  = 1 for follow-up period, = 0 otherwise;  $e$  = 1 for experimental arm, = 0 for control arm;  $p\_chars$  are participant characteristics (e.g, age, gender);  $c\_chars$  are clinician characteristics (e.g, age, gender); clinician indicators will capture differences in clinician approaches; and, study site indicators will capture differences in location of intervention delivery. Random effects (i.e., participants) will account for unmeasured participant characteristics.

We will examine the linear time trend of intervention effects using interrupted time series analysis (Model 2):

$Y = a0 + a1*wk + a2*int\_pr + a3*wk\_aft + a4*e + a5*wk*e + a6*int\_pr*e + a7*wk\_aft*e + \text{other predictors (p\_chars, c\_chars, clinician, study site, etc.)} + \text{random effects}$

Where:  $Y$  = alcohol use dependent variable;  $wk$  = week number starting with 1 for the first week of data collection;  $int\_pr$  = 1 for intervention period, = 0 otherwise;  $wk\_aft$  = # of week after the intervention starts;  $e$  = 1 for experimental arm, = 0 for control arm; and other predictors and random effects as defined in Model 1. Both models will include multilevel clustering to account for repeated measures from the same participant, as well as correlation among participants receiving intervention in the same study site.

For **PTSD symptoms**, the primary outcome is past 30-day total symptom severity on the *PCL-5*. We will compare study conditions on the *PCL-5* total symptom severity score at each time point using a mixed effects model (Model 3). Fixed effects are: study condition (experimental vs. control), time point (four indicator variables with baseline as the reference group), and interaction of study condition and time point. Similar to Models 1 and 2, we will adjust for participant and clinician characteristics; within-clinician, within-site, and repeated measures correlation; and random effects (i.e., unmeasured participant characteristics).

**Sample size and power calculation:** Our proposed sample size is based on pilot results and the limited scope of the proposed pilot RCT. A clinically significant effect should be used for planning a future full-scale RCT. For example, a clinically significant change score for the *PCL-5* is 10 points, equal to an effect size of 0.47 using a standard deviation of 21.2. Our projected sample size of 22 completers per study arm will have 80% power to detect a large effect size (0.80) comparing two means using a two independent sample t-test for the unadjusted group comparisons. To detect a smaller effect size (e.g., clinically significant effect size of 0.47), a larger sample size would be needed, but is not feasible due to the scope of the proposed pilot RCT. We used the unadjusted t-test for the power calculations due to the largely unknown assumptions required to calculate the power for a mixed effects model; however, the mixed effects models will have more power than the unadjusted t-test due to the partitioning of the variance among the various components.

**Analytic plan for potential mechanisms of change.** We will examine potential moderators and mediators of intervention effects. We will compare the two treatment arms on these variables at

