**Analytic plan for preliminary clinical outcomes.** We will compare treatment arms using two primary clinical outcomes at immediate post-treatment and one-month follow-up: (1) past 30-day alcohol use frequency/quantity (from *Alcohol Timeline Followback*); and, (2) past 30-day PTSD severity (from *PCL-5*). For **alcohol use**, outcome variables are: % drinking days per week (i.e., days with 1+ drink); % binge drinking days per week (i.e., days with 5+ drinks for men, 4+ for women); and mean number of drinks per week. These variables will be calculated from daily data collected with the *Alcohol Timeline Followback* for 30 days (4 weeks) prior to the last drink before baseline assessment, throughout the 12-week intervention or waitlist period, and throughout the one-month follow up period. Such a weekly measure will allow for estimation of changes per weekly intervention session in the experimental condition as compared to waitlist control.

Our initial unadjusted group comparisons at immediate post-treatment/week 12 and at the end of the one-month follow-up period/week 16 will use a standard t-test (or Wilcoxon non-parametric test, depending on the outcome distribution). Below, we describe models for analyzing adjusted group differences and for analyzing the longitudinal data. We acknowledge that, with the small sample size of this feasibility study, the following models may be optimistic in terms of their capability to reliably estimate and to test interactions. However, they will provide insight into possible effect sizes for planning the larger clinical trial.

We will first compare differences in weekly drinking between the two study conditions at pre-, during, and post- intervention periods using mixed effects models (Model 1):

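### Models 1–3 adjust the arm comparison for clinician terms that only the experimental arm has, and the plan defines neither the control value nor the adjusted contrast

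*Combined protocol and SAP*

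**What the plan says.** **Clinician terms.** In Section 13 (analytic plan for preliminary clinical outcomes), the list of other predictors in Models 1 and 2 names clinician characteristics, with age and gender as examples, and then adds indicators: "clinician indicators will capture differences in clinician approaches; and, study site indicators will capture differences in location of intervention delivery". For Model 3 (PCL-5) the plan states: "Similar to Models 1 and 2, we will adjust for participant and clinician characteristics; within-clinician, within-site, and repeated measures correlation". No clinician indicators are named for Model 3.

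**Purpose of the models.** The section introduces them with "Below, we describe models for analyzing adjusted group differences and for analyzing the longitudinal data". For Model 1: "We will first compare differences in weekly drinking between the two study conditions at pre-, during, and post- intervention periods using mixed effects models". Model 3 is to compare the conditions on the PCL-5 "total symptom severity score at each time point using a mixed effects model (Model 3"). On their use: "However, they will provide insight into possible effect sizes for planning the larger clinical trial".

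**Who has a clinician.** Section 11 assigns one of four study clinicians to each participant randomised to the intervention. The control arm is assessment only and is offered the protocol after the week-16 assessment, which is the last one analysed. Randomisation is within site and stratified by gender, so every control has a site but none has a clinician.

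**The concern.** A clinician's age, gender or identity has no value for a control in any analysed row. The plan does not nest clinician within the experimental arm, does not give controls a value, and does not say which contrast is the adjusted arm difference. The analyst must choose, and the choice changes what the arm coefficient means, or whether it can be estimated at all.

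The adjusted differences during and after treatment, and the PCL-5 difference at each visit, are what these models are meant to supply. They are also to inform effect sizes for the larger trial. An effect size that depends on an unstated coding is a weak basis for that.

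**Working it through.** The plan gives no figure for Models 1–3 that could be reproduced, so the check is on the design matrices.

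**Inputs from the documents.** 60 participants (taken as 30 per arm); four clinicians in the experimental arm only; site in both arms, run with four locations (Section 6) and three sites (Section 9, Table 2); 4 + 12 + 4 = 20 weekly rows for Models 1–2; five visits for Model 3; PCL-5 SD 21.2 (Section 13).

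**Assumptions.** Clinicians treat 8, 8, 7 and 7 participants. Participant age and gender are covariates. Clinician ages are 35, 42, 51 and 60, with two clinicians of each gender. Within-participant correlation is 0.3, 0.5 or 0.7, and data are complete. The assumed ages, genders and correlations drive the standard errors below. The aliasing in Models 1–2 follows from the algebra.

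**Step 1: aliasing in Models 1–2, controls at zero.** Let d1 to d4 indicate treatment by clinicians 1 to 4.

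- Four indicators: d1 + d2 + d3 + d4 = e.
- Three indicators plus clinician age A: age − A1·d1 − A2·d2 − A3·d3 = A4·d4. This restores the dropped indicator, and the sum is again e. Centring only the characteristics leaves the same result.

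Model 1 with four sites has 6 + 2 + 3 = 11 columns before clinician terms (period and arm terms, participant terms, site terms). The clinician terms add only three new dimensions, so the rank is 11 + 3 = 14. Model 2 starts from 8 + 2 + 3 = 13, giving 16.

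| Clinician terms | Model 1 rank/columns, 4 sites (3 sites) | Model 2 rank/columns, 4 sites (3 sites) |
|---|---|---|
| None | 11/11 (10/10) | 13/13 (12/12) |
| Four indicators + age + gender | 14/17 (13/16) | 16/19 (15/18) |
| Three indicators + age + gender | 14/16 (13/15) | 16/18 (15/17) |

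In the last two rows, b3, b3+b4, b3+b5 and a4 are not estimable. The terms b4, b5 and a5 to a7 are.

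**Step 2: reference clinician, no characteristics.** Model 1 is full rank (14/14; three sites 13/13), but the arm coefficient refers to that one clinician. At correlation 0.5, in SD units and for one choice of reference, the standard error of the during-period difference is 0.365 against 0.190 without clinician terms (0.365/0.190 = 1.9). For the post period it is 0.373 against 0.205 (1.8). The three-site figures are 0.316 (1.7) and 0.325 (1.6).

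**Step 3: Model 3 with uncentred age and gender, controls at zero.** The rank is full (17/17), so the difference is estimable, but it refers to a clinician aged zero. The week-12 standard error without clinician terms is about 21.2 × √(2/30) = 5.5. With clinician gender only it is 6.1–7.3. With uncentred age at the assumed ages it is 19–25 (14–22 if clinicians are spread across sites). With centred terms it is 5.5–5.9. In one simulated data set the week-12 difference was −34.47 with raw age and −13.58 with age shifted by 46.8 years. The arm-by-week-12 term was −4.09 both times, and its standard error (6.48, 5.47, 4.24 at the three correlations) is the same under every coding.

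**Step 4: difference averaged over clinicians.** Add to the arm coefficients the experimental-arm mean of each clinician column times its coefficient. This contrast is estimable in every zero-coded case run. At correlation 0.5 its during-period standard error in Model 1 is about 0.19–0.20, against 0.19 without clinician terms. In the Step 3 data set, the Model 3 week-12 difference at mean characteristics is −12.34, against −12.20 without clinician terms.

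**Step 5: other codings.** Leaving clinician values missing for controls would drop every control row, against Section 13's commitment to analyse all randomised participants. Mapping controls to their site's clinician keeps the arm difference estimable (rank 11 in Model 1). With three sites and four clinicians it needs a further rule for the site that has two.

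**The case against.** The strongest reply is that nothing is lost. A reader might infer from Step 1 that the adjusted arm difference cannot be estimated at all. The documents do not support that: they never set controls to zero, and even under that coding the clinician-averaged difference can be estimated at almost no cost in precision (Step 4). Nor should the standard error of 19–25 be read as what the trial would see. It is for a clinician aged zero, at assumed ages.

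It can also be said that the predictor list is a menu with examples, that mapping controls to a site's clinician is natural with four locations, and that the plan already warns that these models may be optimistic for a small sample. In addition, the treatment effect can be read from the arm-by-period and arm-by-time terms, since b3 is a pre-treatment difference with expectation zero. The unadjusted comparisons also stand: "Our initial unadjusted group comparisons at immediate post-treatment/week 12 and at the end of the one-month follow-up period/week 16 will use a standard t-test".

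Most of this stands, and it limits the point. It does not remove it. Aliasing is not a small-sample problem, and the interactions that the caveat singles out are the part that survives. The plan names neither the averaged contrast nor the mapping, and the location count is unsettled. Fitting the listed terms as written gives aliased or reference-dependent level differences, or drops the controls.

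**Conclusion.** The point holds for the adjusted level comparisons: Model 1's arm difference in each period, a4 in Model 2, and Model 3's difference at each visit. Under zero coding for controls, the coefficients in Models 1–2 are not estimable with four indicators, or with three indicators plus characteristics. With a reference clinician alone they describe one clinician, with a standard error about 1.6 to 1.9 times as large in the layouts shown. In Model 3 the difference depends on how the characteristics are centred, and the inflation depends on clinician ages and genders that the documents do not give.

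The defect is an undefined contrast and an undefined control value, not missing information in the data. Change-from-baseline contrasts and the unadjusted week-12 and week-16 tests remain usable, provided that controls are kept and clinician terms are constant over time. It should be corrected before the models are programmed.

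**What to change.** Remove clinician indicators and clinician characteristics from the between-arm Models 1–3. Keep site and gender, which are the randomisation factors.

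If clinician terms are kept, set them to zero for controls and do one of the following, stated in the plan:

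- centre all of them, indicators as well as characteristics, within the experimental arm; or
- define the adjusted arm difference as the one averaged over the experimental arm's clinicians.

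In either case, explore clinician differences within the experimental arm only, and reconcile the four locations of Section 6 with the three sites of Table 2, because site stays in the models. The change costs wording and code. It needs no data and no participants.

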**Study Conditions.** After enrollment, the Study Assessor will conduct the baseline assessment via videophone. Participants will then be randomly assigned to one of two conditions: (1) *Seeking Safety + Signs of Safety* toolkit, or (2) assessment-only waitlist control. Randomization will occur within each study site and stratified by gender. The Biostatistician will generate a computerized random number series and place numbers in individual sealed opaque envelopes. The RC will open an envelope to randomly assign a treatment condition to the participant. Both the PI and Study Assessor will be blind to study condition. (*Note: the Study Assessor will remain blind to study condition until the end of the post-treatment assessment, at which point she will*

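### Model 2 gives each randomized arm its own pre-randomization level and slope from about four weekly points, which makes the trend coefficient a7 several times noisier than it need be and the week-12 arm difference about 1.2 to 1.6 times noisier

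*Combined protocol and SAP*

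**What the plan says.** Section 13 (analytic plan for preliminary clinical outcomes) introduces the model with "We will examine the linear time trend of intervention effects using interrupted time series analysis (Model 2". Its arm terms are a4 (arm `e`), a5 (`wk`×`e`), a6 (`int_pr`×`e`) and a7 (`wk_aft`×`e`). The time variables are defined as follows:

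- `wk` is the "week number starting with 1 for the first week of data collection".
- `int_pr` is 1 "for intervention period, = 0 otherwise".
- `wk_aft` is the number "of week after the intervention starts". Its value in the follow-up weeks is not stated.

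Model 1 has a follow-up indicator `fu_pr`; Model 2 does not. The drinking data run "for 30 days (4 weeks) prior to the last drink before baseline assessment", and then "throughout the 12-week intervention or waitlist period, and throughout the one-month follow up period". Section 11 (Study Conditions) puts the baseline assessment first: "Participants will then be randomly assigned to one of two conditions". The random effects are described as participant effects, with clustering by site. No variances, standard errors or power are given for Model 2.

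**The concern.** Arm-specific pre-period levels and slopes belong in an interrupted time series that compares non-randomized groups, because those groups may already differ in level and trend. Here every pre-period week lies before assignment. The true arm differences a4 and a5 are therefore zero by design, and what the model estimates for them is chance variation.

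The cost falls on a7. It is not the slope difference between the arms during treatment. It is that difference minus a pre-period slope difference fitted to about four points per person. If a7 is read as the linear trend in the intervention effect, most of its uncertainty comes from estimating a quantity already known to be zero. The plan wants these models to supply effect sizes for the larger trial, and an a7 with that much avoidable noise is a poor planning figure.

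**Working it through.** **Plan's own figure.** None exists for Model 2. The only power statement (80% at 22 completers per arm, effect size 0.80) concerns the unadjusted t-test. An exact two-sided 5% t-test, sidedness and level being assumed, gives 73.6%. That is a separate matter, and nothing below depends on it.

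**Inputs from the documents.** 4 pre-period weeks, 12 treatment or waitlist weeks, about 4 follow-up weeks; a participant random effect; 60 enrolled (30 per arm), 22 completers per arm.

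**Assumed, because the plan gives no variances.** Total SD 1, half of the variance between participants, independent weekly residuals (variance 0.5) in the base case, complete data, no covariates.

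**Step 1: a7.** A slope over k weeks has residual variance σ²/S, where S is the sum of squared week deviations: S = 5 for 4 weeks and 143 for 12 weeks. With n = 30 per arm:

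- As written: Var(a7) = (2/30) × 0.5 × (1/143 + 1/5) = 0.00690, SE 0.083 SD per week.
- Shared pre-period: Var(a7) = (2/30) × 0.5 × (1/143) = 0.000233, SE 0.015.
- Ratio = √(1 + 143/5) = 5.44, whatever n or the variance split. With 22 per arm the SEs are 0.097 and 0.0178.

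**Step 2: how far the ratio depends on assumptions** (generalized least squares).

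| Covariance and weeks used | SE(a7), as written ÷ shared pre-period |
|---|---|
| Random intercept, 12 treatment weeks | 5.44 |
| Same with AR(1) residuals 0.3; 0.6 | 4.7; 4.0 |
| Random intercept, plus 4 follow-up weeks, `int_pr` = 1 there | √(1 + 340/5) = 8.31 |
| Same, `int_pr` = 0 there as defined, `wk_aft` still counting | 10.4 to 10.8 |
| Large random slopes | 2.2 to 2.4 |
| `wk_aft` reset to 0 in follow-up, no `fu_pr` | 1.03 to 1.13 |

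**Step 3: on-treatment slope difference, a5+a7** (30 per arm, 12 treatment weeks; random intercept, then AR(1) 0.3 and 0.6). SE as written: 0.015, 0.019, 0.022. SE of the same quantity with a shared pre-period: 0.015, 0.019, 0.021. There is almost nothing to gain.

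**Step 4: arm difference at treatment week 12.** In Model 2 as written this is a4 + 16×a5 + a6 + 12×a7. Random intercept, 30 per arm:

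- As written, variance per participant = 0.5 + 0.5 × (1/12 + 5.5²/143) = 0.6474. SE = √(2 × 0.6474/30) = 0.21 SD.
- Shared pre-period: the pre-period mean (variance 0.5 + 0.5/4 = 0.625, covariance 0.5 with the week-12 value) works as a baseline adjustment. Variance = 0.6474 − 0.5²/0.625 = 0.2474. SE = √(2 × 0.2474/30) = 0.13 SD.
- Ratio about 1.6. With AR(1) 0.3 and 0.6 the SEs are 0.22 against 0.16 and 0.24 against 0.19, so the ratio falls to about 1.2.

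**Step 5: is dropping the terms safe in follow-up?** Not by itself. Suppose the true effect grows to 0.80 SD at week 12 and stays there. If `wk_aft` resets to 0 and there is no `fu_pr`, the reduced model has no term for a follow-up arm difference and returns a week-12 effect of 0.23 to 0.44 SD. Model 2 as written returns 0.75 to 0.80.

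**The case against.** The case on the other side is substantial.

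First, the loss belongs mainly to one coefficient. A reader might infer that Model 2 cannot show a drinking trend at all: for growth to 0.80 SD by week 12 (0.80/12 = 0.067 SD per week), a7 has power of only about 12% (0.067/0.083 = 0.8 standard errors). The documents do not support that reading, because the same fit yields a5+a7, for which 0.067 is at least 0.067/0.022 = 3.0 standard errors (power about 86% or more).

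Second, a reader might quote an SE of 1.0 to 1.1 SD for a6 + 12×a7 as the precision at week 12. That quantity is the departure from an extrapolated pre-trend, not the arm difference, and the plan never says it will be reported.

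Third, no single multiplier follows from the documents. It depends on a covariance that the plan does not specify and on follow-up coding that it leaves open.

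Fourth, Model 2 is one of several analyses in a feasibility pilot. The initial week-12 and week-16 comparisons are t-tests or Wilcoxon tests, Model 1 extrapolates no slope, and Section 13 warns that these models may be optimistic about interactions.

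All four points stand as limits on the size of the problem. They do not remove it. The plan does not name a5+a7 or the week-12 arm difference as the result to report, so a7 is the coefficient a reader would take. The general caution concerns sample size, whereas this loss comes from the parameterization and is recoverable from the same data. The statement in Section 13 that the mixed models will have more power than the t-test is not supported for a7.

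**Conclusion.** The point holds as an inexpensive improvement to a secondary model. Model 2 estimates two arm differences that randomization sets to zero in expectation. As a result SE(a7) is inflated about 5.4 times over the 12 treatment weeks with a participant random intercept, and about 2 to 10 times across the covariances and follow-up codings tried. It is hardly inflated if `wk_aft` resets to 0 in follow-up with no `fu_pr` term. For the week-12 arm difference the avoidable inflation is about 1.2 to 1.6 times; for the on-treatment slope difference it is close to none.

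The structural part rests on the documents alone. The sizes rest on assumed variances: the random-intercept ratio for a7 does not depend on the variance split, but the week-12 figures do. No main conclusion of the pilot depends on a7.

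**What to change.** 1. Remove a4×`e` and a5×`wk`×`e` from Model 2, so that both arms share one pre-randomization level and slope. Keep `int_pr`×`e` and `wk_aft`×`e` as the treatment terms.
2. Settle follow-up at the same time. Either limit Model 2 to the pre-period plus the 12 treatment weeks, or add `fu_pr` and `fu_pr`×`e` and state how `wk_aft` is coded in follow-up. Step 1 should not be made without this.
3. Name the results to report: the model-based arm difference at treatment week 12 and the on-treatment slope difference, each with a 95% CI.
4. Keep the unrestricted Model 2 as a sensitivity fit.

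The cost is SAP wording and one extra restriction or term for follow-up. Chance baseline imbalance would then be handled through the shared-baseline model instead of arm-specific terms. No data collection changes.

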### 25. LOCAL NUMBER OF SUBJECTS

We will enroll 60 Deaf adults from Massachusetts. Based on pilot results, we anticipate at least 45 participants will be retained through immediate post-treatment (60 enrolled participants x a conservative 0.75 retention rate), or 22 participants per treatment arm. This post-attrition sample size falls within the guidelines for a pilot RCT behavioral therapy study - “15 to 30 participants per cell” - and is “based on the pragmatics of recruitment and the necessities for examining feasibility.”

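### The plan's one power figure (80% for 22 completers per arm at d = 0.80) states no alpha or sidedness and is 74% at two-sided 5%; the claim that the mixed models will do better is unsupported as worded.

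*Combined protocol and SAP*

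**What the plan says.** Section 13 (Sample size and power calculation) gives the document's only numerical power statement: "Our projected sample size of 22 completers per study arm will have 80% power to detect a large effect size (0.80", for an unadjusted comparison of two means by t-test. The 22 comes from Section 25: 60 enrolled at 75% retention is 45, or 22 per arm.

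The paragraph explains that the t-test was used "due to the largely unknown assumptions required to calculate the power for a mixed effects model", and the same sentence goes on to say that "the mixed effects models will have more power than the unadjusted t-test due to the partitioning of the variance".

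The PTSD model (Model 3, Section 13) has fixed effects for condition, "time point (four indicator variables with baseline as the reference group), and interaction of study condition and time point". It adds that "we will adjust for participant and clinician characteristics; within-clinician, within-site, and repeated measures correlation".

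Two caveats appear elsewhere. Section 13 (Analytic plan for preliminary clinical outcomes) concedes that "the following models may be optimistic in terms of their capability to reliably estimate and to test interactions". Section 25 describes the post-attrition sample size as "based on the pragmatics of recruitment and the necessities for examining feasibility".

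**The concern.** A power figure can be checked only if the test, sample size, effect, alpha and sidedness are all known. Here the last two are missing. Under the usual convention of two-sided 5%, the stated inputs do not give 80%.

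The sentence on the mixed models adds to the problem. It asserts that they have more power than the t-test while saying that the assumptions needed to calculate it are largely unknown. A reader may conclude that 80% is a floor which the planned models will exceed. Neither part of that is established.

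At stake is how far the pilot's preliminary efficacy comparisons can be relied on, and whether those planning the full-scale trial can take the figure at face value. The safety and conduct of the pilot are not affected.

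**Working it through.** **Inputs from the plan.** n = 22 per arm, d = 0.80, two-sample t-test, PCL-5 SD 21.2 (all Section 13); 60 × 0.75 = 45 completers (Section 25). Alpha and sidedness are not given, so both usual readings are tried.

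**Step 1: the stated figure.** Degrees of freedom are 22 + 22 − 2 = 42. The noncentrality parameter is d × √(n/2) = 0.80 × √11 = 2.653. Exact power is taken from the noncentral t distribution.

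| Arms | Alpha | Power |
|---|---|---|
| 22 / 22 | two-sided 5% | 73.6% |
| 22 / 23 | two-sided 5% | 74.6% |
| 25 / 25 | two-sided 5% | 79.1% |
| 26 / 26 | two-sided 5% | 80.7% |
| 22 / 22 | one-sided 5%, or two-sided 10% | 83.3% |

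The normal approximation, Φ(2.653 − 1.960), gives 75.6% for 22 per arm, so the choice of formula does not explain the gap. Nor does rounding 22.5 down to 22. Exactly 80% with 22 per arm would need a two-sided alpha of about 7.8%, which is not a conventional level.

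**Step 2: what 22 per arm can detect with 80% power.**

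- Two-sided 5%: d = 0.865, and 0.8646 × 21.2 = 18.3 PCL-5 points.
- One-sided 5%: d = 0.762, and 0.7621 × 21.2 = 16.2 points.
- As stated: 0.80 × 21.2 = 17.0 points.

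Reaching 80% at two-sided 5% for d = 0.80 needs 2 × 26 = 52 completers, and 52/60 = 87% retention against the planned 75%.

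**Step 3: the mixed-model claim.** The plan gives no within-person correlation (rho), intraclass correlation or variance components, so every value below is an assumption. All results are at two-sided 5% with d = 0.80.

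*Arm-by-time term against baseline.* With complete data, equal variances and no covariates, this compares change from baseline. Its variance is 2(1 − rho) times that of the t-test, so the noncentrality is 2.653/√[2(1 − rho)]. On 42 df:

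| rho | Noncentrality | Power |
|---|---|---|
| 0.3 | 2.242 | 59% |
| 0.5 | 2.653 | 74% |
| 0.7 | 3.425 | 92% |

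Below rho = 0.5 this contrast has less power than the t-test. Pooling error df across visits (160 assumed) moves the break-even only to 0.48.

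*Difference at one visit, with covariates.* If participant covariates explained a share R² of outcome variance, the variance falls by the factor (1 − R²). Power is about 76%, 78% and 80% for R² of 5%, 10% and 15%, ignoring clustering.

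*Difference at one visit, with partial data.* Assume 30, 27, 24 and 22 per arm observed at baseline and weeks 4, 8 and 12, equal correlation between visits, 42 df and no clustering. Power is 75.2%, 77.4% and 80.3% at rho 0.3, 0.5 and 0.7. With the same data the arm-by-time term at rho 0.3 has 63.7%.

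*Clinician clustering.* With 22 treated participants over four clinicians (5.5 each), the treated-arm variance is multiplied by 1 + 4.5 × ICC. Without any baseline gain, power is 71.8%, 69.1% and 64.9% at ICC 0.02, 0.05 and 0.10.

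The direction therefore depends on quantities that the plan does not state.

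**The case against.** The strongest reply has four parts.

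First, because alpha is unstated, the certain defect is an omission and not a proven miscalculation; at one-sided 5%, at least 80% power is true. That stands, but two-sided 5% is what most readers will assume, and no conventional alpha gives 80% itself.

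Second, the figure carries little weight. Section 25 rests the sample size on practical grounds. Section 13 says openly that the clinically significant effect of 0.47 is out of reach here and that such an effect should guide the full trial. That stands and limits the consequence. A published figure should still be reproducible.

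Third, Model 3 is described as comparing the arms on the PCL-5 score at each time point, which can be read as a difference at each visit and not as change from baseline. On that reading, with complete data and neither covariates nor clustering, it matches the t-test whatever rho is, and partial data from all randomized participants would add a little. This is fair: the 59% belongs to one contrast at one assumed correlation and is not a forecast. Clustering can still reverse the gain, so the unconditional wording is not rescued.

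Fourth, the plan already warns that the models may be optimistic. That warning concerns reliable estimation and interaction tests. It neither supplies an alpha nor corrects the 80%.

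**Conclusion.** The concern holds. Under two-sided 5% the stated 80% overstates power by about 6 points (80 − 73.6 = 6.4, or 5.4 with 22 and 23 completers). Equivalently, the difference detectable with 80% power is 18.3 rather than 17.0 PCL-5 points. Under one-sided 5% the figure is understated at 83.3%. These results rest only on the plan's own inputs and the two alpha conventions.

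The claim of greater power for the mixed models is not shown to be false. It is unsupported as an unconditional statement, since plausible values of rho, covariate strength and clustering move power in either direction. Those illustrations rest on assumed values.

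This should be corrected, but the impact is modest and the number to enrol does not change.

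**What to change.** 1. State alpha and sidedness in Section 13. If two-sided 5%, restate as about 74% power for d = 0.80, or 80% power for d of about 0.87. If one-sided 5% was intended, say so and give 83%.
2. Replace the unconditional sentence with one saying that the mixed models may have more power, depending on the contrast, the within-person correlation, clustering and the partial data available. State which Model 3 contrast is tested at weeks 12 and 16.

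Both are wording changes. Their only cost is a less favourable stated power if two-sided 5% is meant.

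Optional, and not needed to correct the figure: base the week-12 and week-16 comparisons on a model adjusted for the baseline outcome and the randomization factors (Section 11: "Randomization will occur within each study site and stratified by gender"), with the unadjusted t-test kept as descriptive. The variance factor is (1 − rho²). Ignoring clustering, power reaches 80% at two-sided 5% once rho is about 0.39 (0.381 to 0.387 on 41 to 37 df). Rho is an assumption, and clustering would lower the power. This is a change of analysis but uses data already collected, with no added participants or visits.
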